session, and the first follow-up. The cocaine craving questionnaires will be used to assess post-cue-reactivity craving with the possibility of counselor intervention in the event of clinically significant craving. A response of 6 or 7 on the CCQ Likert scale for questions 3, 4, 16, 33, or 34 or a response of 1 or 2 question 28 would constitute clinically significant craving. Similarly, a response of 9 or 10 on the CCS Likert scale for question 1 would constitute clinically significant craving. The MAI or other NRB clinical personnel will intervene to mitigate craving before discharge if the participant's self-report of craving level arouses concern (in the participant or staff) in the context of conversation. After completing the two-week course of iTBS treatment, the TMT, YMRS, and C-SSRS (since last visit version) will be administered a second time.

Columbia-Suicide Severity Rating Scale (C-SSRS; Appendix 24): An interview-based questionnaire designed to assess acute suicidality. Two versions will be implemented. A baseline measure (with lifetime and past month symptom assessments) will be collected prior to the iTBS intervention and the 'since last visit' version will be collected post iTBS intervention. A researcher trained in administering these scales (e.g., the MAI, LAI, or AI) and approved by the MAI do so, will administer them. The MAI will oversee the training of this scale. If a participant reports any positive answer related to current suicidal tendencies (questions 1-5 for past month at baseline and since last visit assessments), the NIDA-IRP Critical Item Alert System in place in CDW will be initiated to address such responses (<http://irp.drugabuse.gov/PolicyIndex.php>).

Completion time: < 15 minutes.

TBS Monitoring Questionnaire (Appendix 1): An interview-based questionnaire designed to assess symptoms related to iTBS administration. Completion time: < 5 minutes.

Trail Making Task (TMT; Appendix 22): The TMT is a cognitive test where participants are instructed to connect dots in numerical sequence or to alternate between numerical and alphabetical sequences. This task is designed to quickly assess working memory, visual attention, and task switching. Completion time: < 10 minutes.

*Young Mania Rating Scale (YMRS; Appendix 23)*¹²². An interview-based questionnaire designed to assess symptoms of mania. Completion time: < 15 minutes.

4. Follow-Up

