On iTBS days, participants will complete several questionnaires in addition to the iTBS treatments. During iTBS, participants will view cocaine cues (i.e., pictures; Appendix 25) in an attempt to control affective state across participants while also potentially eliciting activation in networks specifically related to cocaine use and substance abuse in general.

Pre-iTBS. Participants will complete a questionnaire about possible side-effects since the last iTBS session (the NIBS monitoring questionnaire) and a questionnaire about their affect (the modified version of the PANAS; see Appendix 1 & 15). Participants will also complete Trails A and B (Appendix 22) prior to and following iTBS administration each day. These assessments will also be collected at baseline prior to any TMS or iTBS administration to assess a true baseline measure for each participant. Also, measures of mania (Young Mania Rating Scale [YMRS]; Appendix 23), suicidality (Columbia-Suicide Severity Rating Scale: Baseline [C-SSRS]; Appendix 24) and depression (MADRS¹¹²; Appendix 14) will be collected prior to the first iTBS session in CD.

iTBS Session. Resting motor threshold will be determined daily, as described below. Recruitment curves will be measured during orientation (HC and CD), and in the CD group, before the first iTBS administration on iTBS day 1, after the last iTBS administration on iTBS day 10, and each of the follow-up visits with an MRI scan. Approximately 1 hour.

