Post-iTBS. At the end of the visit, participants are asked to fill in a questionnaire about possible side-effects (the NIBS monitoring questionnaire), a questionnaire about their affect (the modified version of the PANAS; see Appendix 1 & 15), questionnaires assessing the blind will be administered (Appendix 46), and an assessment of pain will be administered (Appendix 46). The iTBS administrator will also fill out an assessment of the blind (Appendix 47). Questions about blinding and pain levels will be asked of the participant after the last iTBS session. Questions about blinding will be asked of the TMS operator after the last iTBS session. Participants will also complete Trails A and B (Appendix 22) after the final iTBS administration each day, prior to discharge. After the final iTBS session (i.e., on Day 10, prior to discharge), measures of mania (Young Mania Rating Scale [YMRS]; Appendix 23), suicidality (Columbia-Suicide Severity Rating Scale: Baseline [C-SSRS]; Appendix 24) and depression (MADRS¹¹²; Appendix 14) will be collected. Contact attempts will be made by phone 1-3 days after the last iTBS session to assess any acute behavioral or health related changes from treatment (Appendix 1).

5. Post-Treatment Follow-Up

Ongoing follow-up will be attempted for 24-weeks post-treatment and will include urine samples for implementation of CM, as outlined in Table 1, and assessments of substance use (participants may repeat some or all characterization measures and assessments of drug use). MRI scans will be performed about one month and three months after the start of iTBS treatments (on approximately visits 19 and 36) to assess neural plasticity related to abstinence, reduction, or continuation of drug use post-treatment. The ASI will be scheduled to be completed within 1-week of all follow-up

visits that include an MRI scan, along with the three mood measures (YMRS, MADRS and C-SSRS). ASI will also be completed at the final visit of the study. The first 12-weeks post-treatment follow-up appointments will be in-person. The next 12-weeks will consist of once-a-week phone contact attempts and once-a-month in-person visits to assess drug use post-treatment. Additional attempts will be performed only through means approved by the participant. These may include such alternative methods as text and e-mail if phone contact is not successful.

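### The Expanded Study names the Baseline C-SSRS for Day 10, so suicidality during iTBS is not cleanly identified in participants who were already past-month positive before treatment

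*Combined protocol and SAP*

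**What the plan says.** The combined protocol and SAP describes the C-SSRS in two places.

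- **Pilot, Section II.E.i.3 (Orientation and iTBS Sessions).** This is the only place where the versions are defined: "A baseline measure (with lifetime and past month symptom assessments) will be collected prior to the iTBS intervention and the 'since last visit' version" is given after iTBS. The same section repeats that, once the two-week course is over, the "C-SSRS (since last visit version) will be administered a second time". It also ties the critical-item alert to "questions 1-5 for past month at baseline and since last visit assessments".
- **Expanded Feasibility Study, Section III.G.i.4 (iTBS Sessions).** The Pre-iTBS paragraph names "suicidality (Columbia-Suicide Severity Rating Scale: Baseline [C-SSRS]; Appendix 24) and depression" among measures that "will be collected prior to the first iTBS session in CD". The Post-iTBS paragraph opens its list with "After the final iTBS session (i.e., on Day 10, prior to discharge), measures of mania" and then names the C-SSRS in the same words as the Pre-iTBS paragraph, including the word Baseline: "Columbia-Suicide Severity Rating Scale: Baseline [C-SSRS]; Appendix 24) and depression".

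The Expanded Study section never mentions the since-last-visit version. Section III.G.i.5 (Post-Treatment Follow-Up) repeats the C-SSRS around the follow-up visits with an MRI scan and names no version.

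**The concern.** Monitoring the safety of iTBS in cocaine-dependent participants is Aim 5 (Section III.C). For that aim, the useful question on Day 10 is what happened since the pre-treatment assessment. A form that looks back over a lifetime and over the past month asks something else when the course lasts two to three weeks: part of the past-month window lies before the first session, and the lifetime part covers all earlier time.

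Staff who follow the Post-iTBS paragraph as written would use that form. Taken alone, a positive Day-10 answer could then describe the weeks before treatment. The alert rule is also left unclear. It is written for past-month answers at baseline and for since-last-visit answers, and it does not describe a Baseline form given after treatment. Which Day-10 answers count as current is therefore not stated, and the paragraphs must be reconciled.

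**Working it through.** **1. Versions side by side**

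| Time | Pilot (II.E.i.3) | Expanded Study (III.G.i.4 and 5) |
|---|---|---|
| Before first session | Baseline | Baseline |
| After last session | Since last visit | Baseline |
| Follow-up MRI visits | Not applicable | Collected, version not named |

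**2. How far the Day-10 window reaches back**

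The plan gives no figure on this point, so there is none to reproduce. The inputs are:

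- *w*, the length of the past month. The documents give no day count, so 28 to 31 days is assumed.
- *t*, the calendar span of the course. Section III.G.i.4 schedules ten treatment days in two weeks where possible and allows up to three. Ten weekdays span 5 + 2 + 5 = 12 days, two full weeks 14, and the maximum 21.

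Pre-treatment days inside the Day-10 window = *w* − *t*, taking the pre-treatment form as completed on the day of the first session:

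| *w* | *t* = 12 | *t* = 14 | *t* = 21 |
|---|---|---|---|
| 28 | 16 | 14 | 7 |
| 30 | 18 | 16 | 9 |
| 31 | 19 | 17 | 10 |

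The overlap is 7 to 19 days, from 7/28 = 25% to 19/31 = 61% of the window. These are shares of calendar days. They are not rates of misclassified participants.

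**3. What the two Baseline forms show together**

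This reading applies question by question to the past-month answers.

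- *Negative before, negative on Day 10:* nothing reported in either window.
- *Negative before, positive on Day 10:* new onset. The overlapping days were already reported negative, so the positive must come from after the pre-treatment assessment.
- *Positive before, negative on Day 10:* nothing in the overlap or during the course. The earlier symptoms lay before the Day-10 window.
- *Positive before, positive on Day 10:* ambiguous. The Day-10 answer may reflect symptoms that persisted into the course, that stopped in the overlap before the first session, or that stopped and came back.

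Only the last cell is unresolved. It need not be empty: the exclusion list in Section III.F.iii has no suicidality criterion, and it says that mild unipolar depression does not exclude.

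**4. Could the Baseline form miss symptoms during treatment?**

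No. The shortest assumed window (28 days) is longer than the longest permitted course (21 days), so the whole course is covered.

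**5. Why the follow-up version should be named**

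Visit 19 is in week 6. The second scan day is in week 14 (visit 40, Section III.E) or week 12 (visit 36, Sections III.G.i.3 and III.G.i.5; sample 24 in Table 1). The interval is (12 − 6) × 7 = 42 to (14 − 6) × 7 = 56 days. If the Baseline form were used there, a 30-day window would leave about 12 to 26 days covered only by the lifetime part, which does not date events. This is conditional, because the plan does not say which form applies.

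**The case against.** The strongest reply is that the same form is given before the first session, so the two can be compared. That stands: it resolves every case except the participant who is past-month positive both times. A reader might infer that suicidality arising during iTBS cannot be separated from earlier symptoms in anyone. The documents do not support that reading.

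Second, suicidality monitoring does not rest on this form alone. The MADRS is collected at the same two times, and endorsing suicidality on it raises a flag that must be dealt with before the participant leaves (Section IV.C). Daily staff observation, the NIBS monitoring questionnaire and a call one to three days after the last session add to this. This also stands as to detection, but none of these dates a C-SSRS answer.

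Third, the Post-iTBS wording repeats the Pre-iTBS wording and may be a copying slip. Appendix 24 is cited for an instrument with two versions, so the citation does not say which is meant. The Pilot is also complete, and its text need not bind the Expanded Study. All of this is possible, but the Pilot text is the only definition of the versions, and the Expanded Study text says Baseline in plain words.

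Fourth, a reader might infer that symptoms from before treatment would dilute an active-sham difference. No planned test names the C-SSRS. The chi-square comparisons in Sections IV.C and IX.C cover seizures, Trails B, clinically significant adverse events and worsening cocaine use. Section III.G.vi mentions questionnaire data only in general terms.

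**Conclusion.** The point holds in limited form. The Expanded Study names the Baseline C-SSRS for Day 10, contrary to the version scheme in the Pilot text. Its past-month window takes in about 7 to 19 pre-treatment days, on the assumption of a 28-to-31-day month and a course of 12 to 21 calendar days. In participants who were past-month positive before iTBS and are positive again on Day 10, persisting, resolved and recurring suicidality cannot be told apart. New onset remains readable in those who were past-month negative, and no part of the course falls outside the window.

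The overlap should not be presented as a bias size. The documents give no frequency of past-month suicidality at baseline, so the number of ambiguous participants is unknown. It would also be wrong to say that the follow-up MRI visits use the wrong form, because the plan names none there. Whether the Day-10 wording was deliberate cannot be settled from the documents.

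**What to change.** Reconcile the C-SSRS description in Section II.E.i.3 with the Pre-iTBS and Post-iTBS paragraphs of Section III.G.i.4, so that the Day-10 form covers the interval since the pre-treatment assessment, as the Pilot text does. State in Section III.G.i.5 which version applies at the follow-up MRI visits. In the same edit, say which answers the alert rule refers to at each time point.

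An interval-based form would show whether symptoms were present since the pre-treatment assessment, and so separate resolved symptoms from the rest. Telling persistence from recurrence within the course would still need the timing of symptoms to be recorded.

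The cost is protocol wording. The version is already specified in the Pilot text, and no extra visit is needed. For participants already assessed, record which form was actually used on Day 10 and, where it was Baseline, read it against the pre-treatment form question by question.

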or completed protocols where task reproducibility was not compromised in several of the tasks we will implement here (i.e., Flanker, Stroop, the decision making task, MID, or SSRT). In addition, it should also be noted that participants will receive extensive and repeated training on all tasks throughout the protocol. This training, taking place on multiple days, is expected to help mitigate the impact of in-scanner practice effects on the measures of interest. The presence of a group receiving CM and sham-ITBS will also help control for any practice effects. Nonetheless, potential confound of practice effects will be examined and if observed, may be a potential limitation of the study.

2. Relationship to Other Protocols

All participants in this protocol will first enter the approved NIDA-IRP general screening protocol. Data from the screening protocol will be used to determine eligibility. Every participant in the Expanded Feasibility Study will also be enrolled in protocol 10-DA-N457 to obtain characterization information. Data obtained under the screening protocol and 10-DA-N457 may be shared with this and potentially other protocols.

vi. Statistical Analysis

Behavioral performance measures (e.g., response time, error rate, and hit rate) on each of the cognitive tasks as well as questionnaire data from each of the experimental conditions will be compared both within and between experimental groups using mixed, repeated-measures ANOVA, and linear mixed models. When assessing the statistical results from the behavioral and questionnaire data, a standard α -level of 0.05 will be used. Alpha-levels for multiple comparison follow-up tests will be corrected using an appropriate method (e.g., Bonferroni, Tukey, Scheffe).

Without knowing the final breakdown of completers and non-completers, we cannot definitively outline the planned analyses, but several options are possible. For example, if a substantial number of participants fail to complete 10 iTBS treatment days, this group could be included as a separate group for comparison. Further analyses with this group would depend on the characteristics of the group vis a vis the 10 iTBS treatment

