day completers. On the other hand, if most participants fail to complete 10 iTBS treatment days, all participants who complete five days of treatment would be considered in the final analysis and the number of iTBS treatment days would be included as a covariate. In the end, the protocol allows for data collection to be maximally flexible while allowing the measurement of iTBS efficacy in treating cocaine use disorder.

An outline of proposed imaging analysis steps is presented below. Current techniques are outlined with the understanding that while these data are collected, new analysis techniques may be developed. These new techniques may be better suited to answer our questions with the data collected. Therefore, the specific analyses carried out at the end of this protocol are subject to change to reflect the most advanced and appropriate analysis techniques available.

The imaging data will be pre-processed and analyzed with Analysis of Functional Neuro-Images (AFNI¹⁶⁰). All functional images will be directly registered upon high resolution MPRAGE anatomical scans obtained during the same imaging session. Location and intensity of activations from individual and/or grouped data will be translated into 3D stereotaxic coordinates¹⁶¹. Functional images of activation-induced BOLD signal changes will be determined using cross correlation or multiple regression analyses^{162, 163}. The specific statistical analyses to be performed on the fMRI 3-D datasets will be dictated by the nature of the factors involved and the specific scientific question addressed. For example, ANOVA models (3dANOVA, 3dANOVA2, 3dANOVA3) can be used to test for differences between participant groups or iTBS condition. Differences in structural and functional measures between CD and HC participants will be assessed using between group comparisons (e.g., independent samples t-tests). Differences within the CD group across sessions will be assessed using within group comparisons (e.g., dependent samples t-tests). Correlation and multiple regression approaches will be used to test for an association between clinical assessment measures and task-specific neural measures (e.g., correlation between cocaine craving scores and neural activation in the striatum).

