Nonetheless, there is a single published report in a sample of participants with major depression where functional connectivity was measured pre- and post-rTMS treatment¹⁶⁶. In this report, the mean functional connectivity pre-TMS (0.38 z-scored connectivity) was greater than post-TMS (0.22 z-scored connectivity) with an average standard deviation of 0.17 z-scored connectivity. We calculated the effect size to be 0.91. This effect size is likely unrealistically high due to 'double-dipping' in their analyses¹⁶⁷, a small sample size, and publication bias toward significant effects, all of which affect the effect size calculation and generalizability.

To better assess a more realistic effect size based on these findings, we simulated an effect size (N =10,000) based on the published means and standard deviations. The effect size that falls 1 standard deviation below the mean was 0.64. This effect is remarkably close to a published report comparing functional connectivity between healthy controls and cocaine users⁴⁴ without a TMS intervention (calculated effect size of 0.67).

Together, when assessing functional connectivity differences post-iTBS treatment between active and sham groups, we conservatively select an effect size 0.65 to capture a reliable effect while reducing the likelihood of committing a Type II error and a power level (1- β) of 0.8 to achieve an appropriate balance between the ability to detect significant differences and the number of participants needed. Therefore, for power analysis calculations (i.e., Statistical Analysis Plan), we anticipate a mean functional connectivity measure post-iTBS for the sham group to be 0.210 z-scored connectivity and active group to be 0.405 z-scored connectivity with a standard deviation of 0.299 z-scored connectivity, which produces an effect size of 0.65 and an estimated sample size needed per group to be 30 with a one-tailed *t*-test assuming a *p*-value of .05. We anticipate approximately 60% retention rate by visit 19, based on previous NIDA protocols. Therefore, 100 CD participants will be recruited at baseline, 45 active and 45 sham iTBS, to acquire the necessary 30 participants in each group for analysis.

IV. COLLECTION AND STORAGE OF HUMAN SPECIMENS OR DATA

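### Nothing locks the imaging analysis or the analysis set for the powered active-versus-sham contrast before arm codes can be seen, so its one-sided 0.05 is not protected across those choices

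*Combined protocol and SAP*

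**What the plan says.** All of the following is in section III.G.vi (Statistical Analysis) unless stated.

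- **Imaging methods.** The analysis steps are given as an outline. Newer techniques may emerge while data are being collected, and so "the specific analyses carried out at the end of this protocol are subject to change". On the choice of model, "The specific statistical analyses to be performed on the fMRI 3-D datasets will be dictated by the nature of the factors involved" and by the scientific question; ANOVA programs are offered as examples.
- **Analysis set.** Because the split of completers and non-completers is not yet known, "we cannot definitively outline the planned analyses, but several options are possible". If a substantial number do not finish ten treatment days, they may form a separate comparison group. If most do not finish, everyone with five days enters the final analysis with number of days as a covariate. Neither trigger has a number.
- **Powered contrast.** The sample size is set for "when assessing functional connectivity differences post-iTBS treatment between active and sham groups". The assumed means put the "sham group to be 0.210 z-scored connectivity and active group to be 0.405 z-scored connectivity", with SD 0.299. The result is "an estimated sample size needed per group to be 30 with a one-tailed" t-test, "assuming a *p*-value of .05", at a power "of 0.8 to achieve an appropriate balance between the ability to detect significant differences and the number of participants needed".
- **Test named elsewhere.** Another paragraph assigns paired t-tests to differences between active and sham conditions.
- **Error control.** AlphaSim is named for multiple comparisons in MRI analyses. A separate sentence corrects follow-up tests on behavioural and questionnaire data.
- **Completers.** Section III.B says the study is powered on completers. Section III.G.i defines a CD completer as ten iTBS days within three weeks plus visit 19.

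**The concern.** A nominal 0.05 belongs to one test chosen without reference to its result. Here the plan expressly allows the imaging method to change at the end of the study and the analysis set to depend on who completes. It sets no date after which the choice is closed and does not ask that the choice be made blind to arm. The contrast affected is the one that fixes the sample size.

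The study is called a feasibility study, but section III.G.vi says the design allows iTBS efficacy to be measured, and section VII says the protocol is intended to determine efficacy. A positive active-versus-sham connectivity result would be read in that light. A reader could not tell whether the reported connection, model and set were the only ones tried.

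**Working it through.** **1. Does the plan's own figure reproduce?** Inputs from the power paragraph of III.G.vi: difference 0.405 − 0.210 = 0.195; SD 0.299; one-sided alpha 0.05; power 0.80.

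- d = 0.195 / 0.299 = 0.652.
- n per arm = 2 × ((1.645 + 0.842) / 0.652)² = 29.1, rounded up to 30. The noncentral t gives 29.8, also 30; power at 30 per arm is 80.3%.
- A two-sided test would need 37 (normal) or 38 (t), so the stated 30 is a one-sided figure for a single test.

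**2. What is fixed for that single test, and what is open?**

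- *Outcome:* functional connectivity after treatment is fixed as a class. Seed, target connection and network are not named.
- *Visit:* implied to be visit 19 through the retention assumption. Resting scans are also taken at the later scan day, and section III.E compares scans 5 to 8 with scans 1 to 3.
- *Pipeline:* AFNI, registration to the same-session structural scan and AlphaSim are named. Further preprocessing is not, and all of it falls under the permission to change.
- *Model:* the power paragraph implies an independent-groups t-test. The paired t-test named for active versus sham conditions could serve the healthy-control crossover, but cannot apply to the parallel CD arms.
- *Analysis set:* completers by default, with two alternatives on unquantified triggers. Section III.G.i offers all later visits and scans to CD participants with at least five treatment days, so the data for the wider set would exist.

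**3. How large could the effect on error be?** The documents give neither the number of candidate analyses, k, nor the correlation of their test statistics, ρ. Both are assumptions here. For k equicorrelated normal statistics under the null, with the most favourable reported,

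error = 1 − ∫ φ(c) · Φ((1.645 − √ρ·c) / √(1 − ρ))^k dc.

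- ρ = 0.7: k = 3 gives 10.3%; k = 5 gives 13.5%.
- ρ = 0.9: k = 3 gives 7.95%; k = 5 gives 9.45%.

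Now take only a choice between completers and a wider set that contains them. If n1 per arm are nested in n2, the two statistics correlate at √(n1/n2), ignoring the days covariate. With assumed sizes and k = 2:

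- 30 in 35: ρ = 0.926, error 6.6%.
- 30 in 40: ρ = 0.866, error 7.1%.
- 20 in 35: ρ = 0.756, error 7.8%.

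**4. What would it cost to keep several candidates and correct for them?** Bonferroni at one-sided 0.05/k, by the t-test: k = 2 needs 38 per arm (power at 30 is 70.0%); k = 4 needs 46 per arm (power at 30 is 59.1%). Locking one analysis leaves 30 per arm.

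**The case against.** The strongest reply is that the plan describes method development, not a search for results. The sentence on change goes on to say its purpose is to use the most advanced and suitable techniques. The sentence on model choice ties the model to the factors and the question, both known before any data, so it is weak evidence of post-hoc selection. Attrition can be counted without outcomes or arm codes. Completers are defined, the power paragraph gives a default test, operators and participants are to be blind to coil side (III.G.iii), and no interim analysis is planned (IX.D).

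Most of this stands, and it rules out three stronger readings that a reader might infer:

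- *That analyses will be picked after seeing results by arm.* No sentence says so. The freedom to change is stated; on whether it is exercised blind, the text is silent.
- *That population and test are wholly open.* There is a default for each. What is missing is the connection, the detailed pipeline, and numbers on the triggers.
- *That imaging error is uncontrolled.* AlphaSim addresses error across voxels within a map.

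The reply does not supply a lock. Coil blinding does not cover analysts. Attrition triggers without numbers can be interpreted after the fact, and AlphaSim does not correct for a choice among maps, measures, models or sets. It is also one of the outlined techniques that may change.

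**Conclusion.** The point holds in this limited form: for the contrast that sizes the trial, the plan permits late change of imaging method and analysis set, names no seed or target connection, and contains no safeguard that the final choice precedes sight of arm codes. The nominal one-tailed 0.05 is therefore not protected across measure, model and analysis set.

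The size is illustrative. Roughly 8% to 13.5% rests on three to five candidates at correlations of 0.7 to 0.9 with the best one reported; 6.6% to 7.8% rests on assumed nested set sizes. If the choice is in fact made blind to arm, there is no such inflation. Given that, and the feasibility label, this should be corrected but does not by itself invalidate the design.

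**What to change.** Replace the sentence that leaves the analyses open with a dated lock, completed before any unblinding of arm codes, of one analysis for the powered contrast. It should state:

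- one seed-target connection and the full preprocessing;
- visit 19 as the time point;
- the analysis set: by default, completers as defined in III.G.i, with any attrition-based switch given a numeric trigger and applied blind to arm;
- sidedness;
- an independent-groups model of post-treatment connectivity, adjusted for baseline resting-scan connectivity. Scans 2 and 3 both include a pre-treatment resting run, so the lock should say which is used.

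The paragraph on paired t-tests should be confined to within-person comparisons. New techniques may be adopted freely up to the lock; anything later is reported as exploratory.

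Baseline adjustment is not needed to cure the timing problem, but it uses data already collected. The cost is a dated section of text and some loss of flexibility after the lock. No further participants or scans are needed, and the 30 per arm stands.
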